4.4.3. Laboratory Data

Laboratory test results will be presented based on the measurements with Système International (SI) units provided by a central laboratory. Unit conversions to SI units will be performed for test results collected from local labs before the raw data is received by the biostatistics team. Additional conversions may be performed at analysis dataset level with appropriate conversion factors if necessary. If a laboratory value is reported using a non-numeric qualifier (e.g., less than (<) a certain value, or greater than (>) a certain value), the given numeric value will be used in the summary statistics, ignoring the non-numeric qualifier, while the original values including non-numeric qualifier will be provided in the data listings.

Results and change from baseline will be summarized with descriptive statistics by transfusion history stratum, nominal time point, laboratory panel (hematology, chemistry, coagulation, urinalysis, and Hb electrophoresis) and parameter. In the event of multiple entries by time point, the latest non-missing value will be used. Only the pre-specified parameters for the Hb electrophoresis panel will be summarized; additional Hb variants reported will be presented in listings only.

All available laboratory data for hematology, chemistry, Hb electrophoresis, coagulation, serology, urinalysis, and pregnancy tests (See Appendix E of the study protocol for further details) will be provided in data listings. Summaries will be done for the listed parameters below only:

- Hematology: Hb, Hematocrit, RBCs, RBW, Absolute Reticulocytes, Reticulocytes (%), MCHC, MCV, Platelets, WBC, Absolute Neutrophils, Neutrophils (%), Abs Lymphocytes, Lymphocytes (%), Abs Eosinophils, Eosinophils (%), Abs Monocytes, Monocytes (%), Abs Basophils, Basophils (%)
- Hb electrophoresis: Hgb A, Hgb A2, Hgb C, Hgb F, and Hgb S
- Chemistry: Albumin, Total Protein, Sodium, Potassium, Calcium, Phosphorus, Chloride, Bicarbonate/CO₂, BUN, Creatinine, Magnesium, Glucose, Amylase, Lipase,

LDH, ALT, AST, Alkaline Phosphatase, Total Bilirubin, Direct Bilirubin, Indirect Bilirubin, eGFR, and GGT

- Coagulation: INR, Prothrombin time, and PTT
- Urinalysis: pH, Specific Gravity

Line plots with mean \pm SE over nominal visits will be included for liver function tests (ALT, AST, ALP, and total bilirubin). eDISH plots of peak AST and ALT versus total bilirubin at the same visit of peak ALT/AST will be included.

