4.5 Dose-Limiting Toxicities Evaluation Period/Definition

Dose-limiting toxicities (DLTs) will be evaluated during the first 28 days of treatment using NCI-CTCAE v5.0.

DLTs are determined by the Investigator and include any of the following AEs that are considered related to etavopivat (ie, all AEs of the specified grades except those that are clearly and incontrovertibly due to underlying malignancy or extraneous causes, eg, intercurrent illness or concomitant medication):

• Non-Hematologic Toxicity

- Erade 3 toxicity with the following exceptions: (1) nausea, vomiting, diarrhea lasting
 72 hours (with optimal medical management and other supportive care); (2) fatigue lasting < 1 week
- Clinically relevant (requiring treatment or with potential clinical sequelae) ≥ Grade 3 non-hematologic laboratory finding. This includes:
 - ≥ Grade 3 electrolyte abnormality that lasts > 72 hours despite adequate management, unless the patient has clinical symptoms, in which case all Grade ≥ 3 electrolyte abnormality regardless of duration should count as a DLT.
 - Note: Grade ≥ 3 amylase or lipase elevation NOT associated with symptoms or clinical manifestations of pancreatitis does not need to be counted as a DLT
- Hy's law as defined by aspartate aminotransferase or alanine aminotransferase (ALT) > 3 × ULN and total bilirubin > 2 × ULN with alkaline phosphatase < 2 × ULN in the absence of a clear alternative explanation
- Inability to tolerate/receive a minimum of 75% of etavopivat scheduled doses during first 28 days of treatment due to an AE of any grade that is considered related to etavopivat, unrelated to underlying malignancy or intercurrent illness, and unrelated to a concomitant medication
- Any death not clearly due to the underlying disease or extraneous causes

• Hematologic Toxicity

- o Grade 4 thrombocytopenia for > 7 days
- o Grade 3 thrombocytopenia with bleeding
- o Grade 4 neutropenia lasting for > 7 days
- o Febrile neutropenia / neutropenic fever

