8.3.6 Serum Chemistry

Chemistry assessments will be performed according to the schedule in Table 1-1 and Table 1-2. A list of serum chemistry tests to be performed is provided (Appendix E).

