8.7.2 Serious Adverse Events

8.7.2.1 Definition

An SAE is any untoward medical occurrence that occurs at any dose that:

- Results in death. Any event resulting in death during the reporting period [from time of the first dose of study drug through 28 days after last dose of study drug] must be treated as an SAE and reported as such.
- Is life-threatening (patient is at immediate risk of death from the event as it occurred) NOTE: this is different than life-threatening severity criteria.
- Requires in-patient hospitalization (formal admission to a hospital for medical reasons) or prolongation of existing hospitalization. NOTE: visits to Emergency Rooms, Urgent Care, Accident/Emergency Units, or visits resulting in brief care under, 'Observation Status', do not meet the criteria of in-patient hospitalization.
- Results in persistent or significant disability/incapacity
- Results in a congenital anomaly/birth defect
- Important medical events that may not result in death, are not life-threatening, or do not require hospitalization may be considered SAEs when, based on appropriate medical judgment, they may jeopardize the patient and may require medical or surgical intervention to prevent one of the outcomes listed in this definition.

The following must be reported as an SAE using the important medical event criterion if no other seriousness criteria are applicable:

- Suspicion of transmission of infectious agents via IMP
- Risk of liver injury defined as alanine aminotransferase (ALT) or aspartate aminotransferase (AST) > 3x ULN and total bilirubin > 2x ULN where no alternative aetiology exists (Hy's law)

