4.4.2. Adverse Events

All AEs will be coded using version 26.1 of MedDRA and will be displayed in tables and data listings using SOC and PT.

Adverse events will be summarized in tables presenting both number and percent of patients as well as number of events and incidence rates (events per 100 patient-years). For the former, a patient is counted once for a given SOC and PT. For the latter, each individual adverse event will be counted separately.

For ongoing patients or patients who have discontinued treatment within 28 days prior to the analysis date, time on study is calculated as (data cut date – date of first dose + 1)/365.25. For patients who have discontinued treatment, time on study is calculated as (date of last dose + 28 – date of first dose + 1)/365.25. Cumulative patient-years are the sum of time on study for all patients in the specified group (e.g. NTD).

Analyses of adverse events will be performed for those events that are considered treatment-emergent, which is defined as any adverse event that emerges or worsens in the period from first dose of study drug to 28 days after the last dose of study drug.

TEAEs will be summarized by SOC and PT by transfusion history stratum and overall for the following categories, unless otherwise noted:

- All TEAEs
- Drug-related TEAEs
- Grade 3 or higher TEAEs

- Grade 3 or higher drug-related TEAEs
- TEAEs leading to study drug discontinuation
- Serious TEAEs
- Serious drug-related TEAEs
- TEAEs requiring dose modification (any dose reduction from 400 mg or temporary interruption in dosing due to an adverse event)

TEAEs will be considered drug-related if assessed by the Investigator as possibly related or related, or if relationship is missing. For summaries of severity, when reporting number and percent of patients, only the maximum severity level will be presented in the severity summaries.

All adverse events occurring on-study will be listed in patient data listings. By-patient listings also will be provided for the following: SAEs, and AEs leading to discontinuation of study drug.

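### The planned eDISH plot takes bilirubin only from the visit of peak ALT/AST, so a patient who meets the protocol's combined liver thresholds at another visit can be plotted outside the Hy's-law quadrant.

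*SAP*

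**What the plan says.** **The display.** SAP section 4.4.3 specifies "eDISH plots of peak AST and ALT versus total bilirubin at the same visit of peak ALT/AST will be included". It gives no quadrant lines and does not say that the axes are multiples of ULN.

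**The thresholds.** Protocol section 8.7.2.1 requires the following to be reported as an SAE: "Risk of liver injury defined as alanine aminotransferase (ALT) or aspartate aminotransferase (AST) > 3x ULN and total bilirubin > 2x ULN", where no other aetiology explains it. Protocol section 4.5 uses the same cut-offs for a DLT in the first 28 days and adds an alkaline phosphatase condition: "> 3 × ULN and total bilirubin > 2 × ULN with alkaline phosphatase < 2 × ULN", again absent a clear alternative explanation. Neither section ties bilirubin to the visit at which the enzyme peaked.

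**The draws.** Protocol section 8.3.6 refers to the schedule of events. Table 1-1 has serum chemistry at Screening and at Weeks 1, 2, 4, 8, 12, 16, 20, 24, 32, 40, 48 and 52.

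**The other liver outputs.** SAP section 4.4.3 plans by-visit descriptive statistics and line plots of mean and standard error, which "will be included for liver function tests (ALT, AST, ALP, and total bilirubin"). It also lists "All available laboratory data for hematology, chemistry, Hb electrophoresis, coagulation, serology, urinalysis, and pregnancy tests". SAP section 4.4.2 tabulates serious TEAEs by SOC and PT and adds: "By-patient listings also will be provided for the following: SAEs, and AEs leading to discontinuation of study drug".

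**The concern.** An eDISH plot screens laboratory data for patients in whom transaminase and bilirubin rise together, before anyone has judged the cause. A reader looks first at the upper-right quadrant and takes an empty one as reassurance.

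Under the planned rule, bilirubin at every visit other than the enzyme peak is ignored. If bilirubin rises after the enzyme has started to fall, the later visit can meet both thresholds without affecting the plot. Scheduled draws are four weeks apart from Week 4 to Week 24 and eight weeks apart from Week 24 to Week 48, so the two maxima need not fall at the same draw.

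The SAP supports the final safety update in an abbreviated report. The planned size is about 45 patients, and the trial stopped early, so 45 is best read as a ceiling. In a group that small, one co-elevation changes how liver safety is read (1/45 = 2.2%).

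**Working it through.** The plan states no figure to reproduce. The check applies the SAP's pairing rule to the protocol's thresholds.

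**Inputs.** Pairing rule: SAP 4.4.3. Thresholds of 3x and 2x ULN: Protocol 8.7.2.1 and 4.5. Quadrant lines are taken from those thresholds because the SAP gives none. All patient values below are assumed.

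**Notation.** For one enzyme, let A(v) be its value and B(v) total bilirubin at visit v, both in multiples of ULN. Let v* be the visit with the largest A.

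- Same-visit co-elevation: A(v) > 3 and B(v) > 2 at some visit v.
- SAP plot: the point is (A(v*), B(v*)), inside the quadrant if A(v*) > 3 and B(v*) > 2.
- Peak-versus-peak plot: the point is (max A, max B), inside if max A > 3 and max B > 2.

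**When the SAP plot misses a case.** Suppose the thresholds are met at a visit v other than v*. Then A(v*) ≥ A(v) > 3, so the enzyme axis is always satisfied. The point is outside if and only if B(v*) ≤ 2.

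**Direction of error.** A point inside the SAP quadrant is itself a same-visit co-elevation, so the SAP rule never adds a false case. Its only error is to miss one.

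**Peak-versus-peak.** If both thresholds are met at any visit v, then max A ≥ A(v) > 3 and max B ≥ B(v) > 2. The point is inside on that enzyme's plot, so no such case is missed. The converse fails: the two maxima can come from different visits.

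**Four assumed patients** (ALT, bilirubin in xULN):

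| Patient | Week 8 | Week 12 | Same-visit co-elevation | SAP point | Peak-versus-peak point |
|---|---|---|---|---|---|
| A | 8, 1.2 | 4, 2.6 | Yes, Week 12 | (8, 1.2) outside | (8, 2.6) inside |
| B | 8, 2.3 | 4, 2.6 | Yes, both weeks | (8, 2.3) inside | (8, 2.6) inside |
| C | 8, 2.3 | 2, 1.6 | Yes, Week 8 | (8, 2.3) inside | (8, 2.3) inside |
| D | 8, 1.2 | 2, 2.6 | No | (8, 1.2) outside | (8, 2.6) inside |

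A is the missed case. B meets the thresholds at a non-peak visit and is still caught, because bilirubin also exceeds 2x at the peak. D shows the price of peak-versus-peak: it enters the quadrant although the two elevations never coincide. With a same-visit marker, A, B and C are marked, D is not, and the count is 3.

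**Two enzymes.** If ALT and AST each have their own plot and peak at different visits, a case missed on one may be inside on the other.

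**The case against.** The strongest case on the other side has four parts.

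1. **The case does not depend on the graphic.** Protocol 8.7.2.1 makes it an SAE even if no other seriousness criterion applies, and Protocol 8.7.5 requires the report within 24 hours. A treatment-emergent case then appears in the serious TEAE tables and the SAE listing, and its chemistry values are listed. This stands for any recognised case. It does not fully replace a laboratory screen. The SAE rule applies only where no alternative aetiology exists. Otherwise, under Protocol 8.7.3, an abnormal value not already part of an AE becomes one only through action on study drug, an intervention, or the investigator's judgement of clinical significance. A laboratory listing leaves the reader to find the pair by eye.

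2. **Same-visit pairing is a defensible choice.** It keeps concurrency, which peak-versus-peak discards. Bilirubin also has other sources here: Protocol 8.2.3 uses unconjugated bilirubin as a haemolysis measure, and Protocol 5.2 sets the bilirubin exclusion above 3.0x ULN for Gilbert syndrome, so a patient can enter already above 2x. This stands against peak-versus-peak alone. It is met by marking same-visit cases.

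3. **Neither plot can establish Hy's law.** Aetiology and, for the DLT definition, alkaline phosphatase are not on the axes. This stands, so any added count must be described as laboratory thresholds only.

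4. **The example is hypothetical.** This stands too. The documents give no rate.

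A reader might infer that every patient who meets the thresholds away from the enzyme peak is plotted outside the quadrant. Patient B shows otherwise, and the second enzyme's plot may catch others. A reader might also infer that eDISH is the only aggregate liver safety output, or that a case would be lost from the report. The TEAE and SAE tables and the listings contradict both.

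**Conclusion.** The display does not match the thresholds it would be read against. A patient with ALT or AST above 3x ULN and bilirubin above 2x ULN at a visit other than the enzyme peak is plotted outside the quadrant on that enzyme's plot exactly when bilirubin at the peak visit is 2x ULN or less. The error runs only towards missing cases.

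No other specified summary joins the two measurements. SAP 4.4 mentions abnormal-result summaries and shift tables, but 4.4.3 specifies none for this pair, and single-parameter tables would not show co-elevation.

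The consequence is limited to a possibly falsely reassuring graphic. It does not affect SAE reporting or the underlying data, and its frequency cannot be estimated from the documents. The conclusion assumes that quadrant lines follow the protocol's 3x and 2x cut-offs and that each enzyme is plotted against bilirubin at its own peak. It is worth correcting before outputs are produced because the change is cheap, not because the safety reporting fails without it.

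**What to change.** In SAP section 4.4.3:

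- Plot each patient's peak on-treatment ALT, and separately peak AST, against peak on-treatment total bilirubin, all in multiples of ULN, with lines at 3x and 2x. State whether the Week 52 safety follow-up draw counts as on-treatment.
- Use a distinct marker for patients with ALT or AST above 3x ULN and total bilirubin above 2x ULN at the same visit.
- Add a count, by transfusion stratum and overall, of patients with that same-visit co-elevation at any on-treatment visit. Label it as laboratory thresholds only, not adjudicated Hy's law.

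**Cost.** A small programming change on chemistry data already collected, with no change to any clinical rule or reporting duty. Some points may enter the quadrant without concurrent enzyme elevation, for instance in Gilbert syndrome or with haemolysis. The marker separates them, and a line of narrative can explain them.

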4.4.4. Vital Signs and Physical Examination

Vital sign results and change from baseline will be summarized with descriptive statistics by nominal time point and transfusion history stratum. Results summarized will include systolic and diastolic blood pressure (BP), pulse, respiratory rate, and temperature.

All physical examination findings and vital sign measurements will be presented in data listings.

4.4.5. Cardiac Monitoring

ECG results (absolute value and change from baseline) will be summarized using descriptive statistics by transfusion history stratum and nominal time point for: RR, PR, QT, QRS, HR, and QT interval corrected using Fridericia's correction formula (QTcF).

ECG data for each patient will be provided in a data listing.

5. CHANGES FROM PROTOCOL

5.1. Endpoint Phrasing Clarifications

No clarifications need to be made.

5.2. Changes to Planned Analyses

For the purpose to support an abbreviated CSR, a selected set of endpoints are included in this SAP. The following analysis populations and endpoints mentioned in the protocol are not included:

Protocol Section 3.2:

- The HI-E for \geq 8 weeks within 16 and 48 weeks of etavopivat
- The HI-E for \geq 16 weeks within 24 and 48 weeks of etavopivat
- Overall response rate (2006 International Working Group [IWG] Criteria) (see protocol Appendix A)
- Duration of response (2006 IWG Criteria)
- Increase in neutrophils and/or platelets counts
- Decrease in ferritin and transferrin saturation (TSAT)
- Decrease in iron chelation therapy
- Overall survival

Protocol Section 3.3:

- PK: maximum observed plasma concentration, time to maximum observed plasma concentration, area under the plasma concentration-time curve from time zero until the last quantifiable time point (AUC0-last), from time zero to infinity (AUC0-inf), for a dosing interval (AUCtau/AUC0-24).
- RBC 2,3-DPG and ATP levels over time

Protocol Section 3.4:

- Change from baseline in Patient-Reported Outcome Measurement Information System (PROMIS) Fatigue Scale at Weeks 16, 24, and 48
- Change from baseline in The Quality of Life in Myelodysplasia Scale (QUALMS) patient-reported outcome assessment at Weeks 16, 24, and 48
- Cell colony analysis of bone marrow progenitors
- Cytomorphology (blast, M/E, and ringed sideroblast determination) and cytogenetics of bone marrow
- Markers of ineffective erythropoiesis and iron metabolism
- Cancer-associated mutations and/or genetic alterations in responding and non-responding patients
- Flow cytometry analysis of terminal erythroid differentiation

Protocol Section 9.2:

- Interim Assessment Set and Per-Protocol Set

5.3. Additional Changes

No patients were anticipated to enter the optional prolonged treatment period. Therefore, related information such as treatment exposure definition and schedule of events are not applicable and are not included in this SAP.

